5. ANALYSIS SAMPLES

The following 3 analysis populations will be identified for this study:

5.1. Modified Intent-to-Treat Population

The modified intent-to-treat (mITT) population includes all enrolled patients receiving at least one dose of treatment and having at least one valid stool collection and CFA post baseline while receiving their assigned study drug.

A stool sample will be considered valid if the date and time associated with the second blue dye marker is recorded, indicating that the stool sample collection is complete.

The mITT population will be used for all analyses of efficacy endpoints.

5.2. Per-Protocol Population

The per-protocol (PP) population is a subset of the mITT population and includes all mITT subjects without major protocol deviations that could impact the efficacy analyses. Protocol deviations will be captured throughout the study and classified as minor or major prior to database lock. Each major deviation will be categorized as either important or not important with respect to the effect on the primary endpoint analysis.

Subjects who are found to be <80% compliant with adrilipase will also be excluded from the PP population. The PP population will be used as supportive to the mITT population.

Prior to database lock, the protocol deviations will be reviewed and the PP Population will be determined.

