6.7 Rationale and Dose Justification

Past *in vitro* studies have shown adrulipase to be relatively acid stable when compared to porcine derived lipases (see Investigator Brochure). However, it is also evident that below pH 4.0, there is increasing inactivation of adrulipase as the pH drops. Work by [Gelfond, et al \(2013\)](#), has shown that in CF patients, the pH in the upper duodenum may be as low as 3.5 for a short period, and the pH in the stomach could be even lower. The gastric emptying time of liquid or solid food may range from 1h-4h or longer and without any gastroprotection adrulipase is likely to have been exposed to low pH in patients with or without gastric acid suppression. Given that in the OPTION study, mean CFA with a dose of 2240 mg/day was 56%, a level below our target of 80%, it was deemed important to provide more protection of adrulipase against acid inactivation in the stomach and upper duodenum to provide adequate adrulipase dose and optimal lipolytic activity in the duodenum. AZ-CF2002 evaluated adrulipase in an enteric capsule, but the results were still below our target of 80%. This was likely due to the inconsistent gastric emptying of the size 0 enteric capsules resulting in adrulipase not being available to mix with and digest food.

Accordingly, for this study, adrulipase as an enteric microgranule formulation in size 00 IR capsules will be employed. Intrinsically, the enteric microgranule formulation is designed to not only provide adrulipase protection against degradation in the gastric environment but also allows for mixing with the food in the stomach and emptying along with the food in the duodenum. The dissolution characteristics of the adrulipase enteric microgranules show lipase availability at pH 5.5 and above, and <15% lipase release below pH 3 i.e., adequate gastroprotection. This matches nicely with our peak enzyme activity at pH 6 and allows rapid release in the duodenum where digestion is taking place.

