- On Day 16 + 5 days (Part 1) or Day 10 + 3 (Part 2) (Visit 6), patients will undergo admission to a controlled supervised facility for stool collection to support the CFA and CNA assessment and weight. A +5-day (Part 1) or +3-day (Part 2) visit window is allowed to accommodate investigative site staff and patients' schedules for the supervised confinement.
- After appearance of fecal stool dye markers has been measured, patients CFA and CNA will be measured under their dose of adrulipase using standardized high-fat meals during the 3-day standardized diet. Additional detailed information provided in the study operations manual should be followed.
- The CFA calculation will be based on the measured fecal fat content in relation to ingested fat quantities during the 3-day stool collection period.

After completion of the initial treatment period during the completion of V6, patients will be instructed to switch their study medication to their prestudy porcine PERT. The stool collection and dietary procedures will be conducted as described in [Section 9.2.4.1.](#) (Instructions for Supervised Confinement)

The following procedures will be performed at Visit 6:

- Begin 72-hour controlled diet

- Focused physical exam to evaluate gastrointestinal tract, heart, and lungs
- Record body height and weight
- Record vital signs while sitting (blood pressure, pulse rate, breathing rate, and temperature)
- Record any changes in AEs and concomitant medication
- Instruct/dispense study drug for confinement period
- Assess and record malabsorption signs and symptoms
- Marker-to-marker stool collection and stool weight (central laboratory will weigh the stool that is collected)
- Collect urine sample for urinalysis
- Perform a urine pregnancy test (urine dip stick), if applicable
- Collect samples for hematology, clinical chemistry, PT/INR, and aPTT
- Collect samples for fasting lipids after patients have been in a fasting status for at least 8 hours (insulin dependent diabetics may be excluded from fasting).
- Record all fat, protein, and dose of study drug taken with every meal and snack during the confinement period
- Verify study drug count on the last day of confinement
- Return adrulipase on the last day of confinement

At the end of the supervised confinement (once the second blue dye marker sample has been collected), patients will return to their prestudy porcine PERT dose.

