9.2.4 *Visit 7: End-of-Study /Early Termination Visit (Part 1 Day 28 ± 2 or Part 2 Day 21 ± 2)*

Patients will return to the clinic for their End of Study visit approximately 1 week after their last dose of study drug. If patients do not complete Visit 6, an Early Termination visit will be held approximately 1 week after the last dose of study drug. The procedures scheduled for the End-of-Study visit are the same as those that should be conducted for the Early Termination visit. The following procedures will be performed at the End-of-Study/Early Termination Visit:

- Focused physical exam to evaluate gastrointestinal tract, heart, and lungs
- Record any changes in AEs and concomitant medication
- Assess and record malabsorption signs and symptoms
- Collect a serum sample for circulating anti-adrulipase antibodies and adrulipase concentrations

- Perform a urine pregnancy test (urine dip stick), if applicable

9.2.4.1 *Instructions for Supervised Confinement for V2 and V6*

Dosing must have occurred for at least 16 days (Part 1) or 10 days (Part 2) prior to the supervised confinements. Beginning at breakfast (the first meal) on Day 1 of the supervised confinement, patients will be placed on a 72-hour controlled diet, with ~25 g fat/meal and 12.5 g fat/snack for a total of 100 g fat/day (3 meals and 2 snacks per day) and a minimum of 1.5 to 2 g of protein per kg of body weight. Although it is preferred to have the patient consume exactly 100 g of fat per day, the fat excretion assay remains valid with a fat intake range within 15% of the goal (i.e., 85 to 115 g of fat per day). The nutritional planning and calculation of dietary fat and nitrogen (protein) intake will be conducted by a qualified dietitian at each site. The actual fat and nitrogen (protein) intake will be calculated from the recorded type and amount of food consumed. A central laboratory will calculate CFA, CNA based on dietary intake and the fat and nitrogen excreted in stool. Stool weight values will also be recorded.

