7.3. Measures of Treatment Compliance

Treatment compliance will be summarized in terms of g/day using a compliance rate and will be displayed overall and by maximum dose of adrulipase received during the study.

The compliance rate will be calculated as:

$$[\text{Actual Dose g/day} / \text{Expected Dose g/day}] * 100$$

The actual dose (g/day) a subject received will be calculated as:

$$[(\text{number pills dispensed} - \text{number of pills returned}) * 0.15 \text{ g}] / \text{number of actual study days on adrulipase},$$

where the number of actual study days on adrulipase is calculated as:

$$(\text{date/time of last adrulipase dose} - \text{date/time of first adrulipase dose}) / 86400 + 1.$$

The expected dose for adrulipase depends on whether the subject titrated to a higher dose during the study, e.g. low dose (1.2 g/day), medium dose (1.95 g/day), high dose (2.4 g/day), and is calculated as:

$$1.2 \text{ g}/(\text{days on low dose}) + 1.95 \text{ g}/(\text{days on medium dose}) + 2.4 \text{ g} (\text{days on high dose})$$

First Wave BioPharma, Inc.
{Statistical Analysis Plan - Protocol #} FWB-CF-2.03

Treatment compliance will be summarized using descriptive statistics.

As described in Section [5.2](#), subjects found to be <80% compliant with adrulipase will be excluded from the PP population.

Individual data for study drug (number of capsules) dispensed and returned, and treatment compliance will be listed for subjects in the mITT population. a

Note that since capsules are dispensed at one visit and returned at one visit (e.g. not separately b

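### Per-protocol compliance rests on a whole-period capsule count, which does not measure dosing during the 72-hour diet that determines Visit 6 CFA, CNA and stool weight

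*SAP*

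**What the plan says.** SAP 5.2 builds the per-protocol (PP) set from mITT patients without major deviations that bear on efficacy, and adds a compliance rule: "Subjects who are found to be <80% compliant with adrilipase will also be excluded from the PP population". SAP 7.3 defines the measure: "Treatment compliance will be summarized in terms of g/day using a compliance rate". Actual dose is capsules dispensed minus returned, times 0.15 g, divided by days on drug from first to last dose. The section adds "Note that since capsules are dispensed at one visit and returned at one visit"; the rest of that sentence is cut off in the text available to me. SAP 9.2.3 then gives a supportive CFA summary in the PP set, and SAP 9.3.3 does the same for CNA.

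Protocol 9.2.4.1 sets the order of events: "Dosing must have occurred for at least 16 days (Part 1) or 10 days (Part 2) prior to the supervised confinements", after which "patients will be placed on a 72-hour controlled diet". During the Visit 6 confinement, Protocol 9.2.3 has sites "Record all fat, protein, and dose of study drug taken with every meal and snack during the confinement period". The SAP's own schedule of events also lists this record, but no SAP compliance derivation uses it.

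**The concern.** CFA at Visit 6 compares fat excreted with fat eaten over the marker-to-marker collection. Protocol 6.7 describes a formulation that "allows for mixing with the food in the stomach and emptying along with the food in the duodenum", so the doses that matter for this measurement are those taken with the diet's meals and snacks. Those three days are a small part of the dosing period, and a whole-period average can hide a large shortfall in them.

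The SAP already accepts that what is taken during the collection matters. Sections 9.2.2, 9.3.1 and 9.3.3 drop the CFA, stool weight and CNA values of a patient who goes back to PERT before the collection ends. There is no matching rule for missed adrulipase. A stool collection counts as valid once the date and time of the second dye marker are recorded (SAP 5.1).

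At stake is the meaning of the PP summary, which Protocol 11.3 names as the sensitivity analysis. It should show CFA in patients who took the drug when CFA was measured. A patient under-dosed during the diet would tend to pull it down.

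**Working it through.** **Inputs**
- Threshold: below 80% is excluded, so exactly 80% stays in (SAP 5.2).
- Capsules per day (Protocol 8.4.1): 3 × meal + 2 × snack. This gives 8, 13, 16 and 22, and at 0.15 g each reproduces the stated 1.2, 1.95, 2.4 and 3.3 g/day.
- Days dosed before the diet: at least 16 (Part 1) or 10 (Part 2). Diet: 3 days (Protocol 9.2.4.1).

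**Assumptions**
- The expected-dose formula in SAP 7.3 is corrected to scheduled grams over the period, divided by days. As printed, it divides grams by days for the low and medium doses. A fully adherent patient on the low dose for 19 days would score 1.2/(1.2/19) = 1900%.
- For Part 2, the rule is extended to 3.3 g/day. The SAP is written to protocol version 1.0 and has no such term.
- Adherence is full before the diet, and the counted period runs to the end of the diet. If a patient took no dose at all after the diet began, the first-to-last-dose period would end before the diet and the rate would be 100%.

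**Constant dose, P days before the diet**
- Two of three diet days missed: (P + 1)/(P + 3) ≥ 0.80 when P ≥ 7. This holds for every schedule meeting the 10- or 16-day minimum.
- All three missed: P/(P + 3) ≥ 0.80 when P ≥ 12. This holds throughout Part 1, but in Part 2 only when the diet starts after 12 or more dosing days.

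**Whole-period compliance by schedule**

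| Schedule (including 3 diet days) | Capsules scheduled | Two diet days missed | All diet doses missed |
|---|---|---|---|
| Part 1, constant dose, 16 + 3 days | – | 17/19 = 89.5% | 16/19 = 84.2% |
| Part 1, 3 low, 3 medium, 13 high days | 24 + 39 + 208 = 271 | 239/271 = 88.2% | 223/271 = 82.3% |
| Part 1, 7 low, 3 medium, 9 high days | 56 + 39 + 144 = 239 | 207/239 = 86.6% | 191/239 = 79.9% |
| Part 1, 13 low, 3 medium, 3 high days | 104 + 39 + 48 = 191 | 159/191 = 83.2% | 143/191 = 74.9% |
| Part 2, 10 + 3 days | 13 × 22 = 286 | 242/286 = 84.6% | 220/286 = 76.9% |
| Part 2, 12 + 3 days | 15 × 22 = 330 | 286/330 = 86.7% | 264/330 = 80.0% |

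In Part 1 with 21 days before the diet, missing two diet days gives 22/24 = 91.7%.

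**Same shortfalls measured on the diet alone:** missing one, two or three of the three days gives 66.7%, 33.3% or 0%.

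**Illustrative effect on the mean.** The documents give untreated-to-treated CFA contrasts only outside CF and with older formulations. In the first-in-man study (Protocol 6.6.1) CFA changed by +6.1 on drug and −6.7 on placebo, which is 6.1 points from baseline or 12.8 between groups. In the Phase 2a study (Protocol 6.6.2) it rose from 46.1% to 62.4%, which is 16.3 points. One fully undosed patient in a PP set of 6 would therefore shift the mean by 6.1/6 = 1.0 to 16.3/6 = 2.7 points. Six is an assumption: about 12 patients are planned, and six were in Part 1 when protocol version 2.0 was written.

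**The case against.** The strongest reply is that other rules stand in the way. PP is a subset of mITT, and SAP 5.1 requires the post-baseline CFA to have been obtained on the assigned drug. A patient who took none during the diet does not plainly qualify. PP also removes major deviations, each classified before database lock by its effect on the primary endpoint; Protocol 11.3 gives the study clinician a role in that judgement. Missed doses at the CFA meals are what such a review would look for. This stands in part: both rules could catch such a patient, but neither states how much dosing is enough, so the decision would be ad hoc in an open-label study.

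A reader might therefore infer too much from the arithmetic: that a patient with no drug during the diet will enter the PP set. The documents do not support that. Passing the 80% rule is not the same as entering PP, and missing every dose does not always pass the rule.

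The event should also be uncommon. Confinement is supervised, every dose is recorded, and the drug count is checked on the last day. That limits how often the gap will matter, but does not close it.

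A reader might also infer that the whole-period rule should be replaced. For example, a Part 2 patient taking 70% of doses over 10 home days and all of them on the diet scores (154 + 66)/286 = 76.9% and is excluded, although CFA was measured at full dose. But the protocol requires 10 or 16 days of dosing before confinement, so excluding poor adherence at home is defensible. A diet-only rule would lose that protection.

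Finally, the PP summary is only supportive, mITT is primary, and no testing is planned. This is correct and limits the consequence.

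**Conclusion.** The concern holds in a limited form: the only numeric compliance rule for PP does not measure dosing in the window that determines the endpoint. Under the stated assumptions, missing two of the three diet days passes in every schedule checked. Missing all of them passes in some schedules and fails in others. How often this would happen cannot be estimated from the documents. The 1-to-3-point shift is an illustration for one extreme patient, not an estimate for CF or for this formulation. The primary mITT analysis does not use the compliance rule and is unaffected by this gap. The point is a mismatch in the supportive analysis that should be corrected because the data to do so are already collected.

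**What to change.** Keep the whole-period rule, with its expected-dose formula corrected and a 3.3 g/day term added for Part 2. In SAP 5.2 and 7.3, add a second PP criterion for CFA, CNA and stool weight:

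- Diet-window compliance = capsules taken ÷ capsules prescribed for the meals and snacks of the Visit 6 72-hour diet, from the meal-level dose record. Because the protocol allows the split across meals to vary by agreement, the denominator should follow the patient's agreed split.
- A value below 80% is classified as an important major deviation. The 80% is carried over from the existing rule and is a choice; over three days it allows 0.2 × 3 = 0.6 of a day's capsules to be missed.
- List both rates beside each Visit 6 CFA value, so that readers can judge borderline patients.

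The cost is SAP wording, one derivation, and cleaning the meal-level dose records to analysis standard. An occasional patient may leave an already small PP set. No visit, dose or mITT definition changes.

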8.6 Study Drug Materials and Management

8.6.1 *Adrulipase*

Study drug Adrulipase will be supplied by First Wave BioPharma for use in the protocol and is limited to investigational use only. Please refer to current Investigator's Brochure for additional information.

Adrulipase is a ~70% pure preparation of LIP2 protein. The concentrated ultra-filtration product obtained from fermentation is mixed with maltodextrin and a generally regarded as safe enteric polymer then subjected to spray drying to produce the drug substance. The drug product is formulated with inactive excipients and formulated in non-animal origin HPMC capsules. Adrulipase will be supplied as 150 mg, size 00 (double zero) capsules.

Adrulipase will be provided in appropriately labeled HDPE bottles.

8.6.1.1 *Adrulipase Shipment, Receipt, and Storage*

Adrulipase will be supplied in bottles to the sites by First Wave BioPharma, in accordance with local requirements. The IMP will be shipped under controlled room temperature condition. The site is responsible for the appropriate storage of the IMP. The IMP must be stored in a secured limited-access area and maintained at controlled room temperature. Controlled room temperature is the temperature maintained thermostatically that encompasses the usual and customary working environment of 20°-25° (68°-77 °F). Excursions between 15° and 30° (59° and 86 °F) that are experienced in pharmacies, hospitals, and warehouses, and during shipping are allowed.

8.6.1.2 *Adrulipase Misuse/Overdose*

Any IMP misuse or overdose associated or not associated with any AE should be reported to First Wave BioPharma, or designee, as an SAE only if it meets the criteria of an SAE. Overdose is considered as dose taken above the prescribed daily dose for the current dosing phase.

8.6.1.3 *Adrulipase and porcine PERT Compliance*

The Investigator is responsible for ensuring compliance. Compliance with adrulipase will be cross-checked with study drug accountability and compliance with pre-study porcine PERT will be evaluated by subject self-report.

8.6.1.4 *Adrulipase Supply, Resupply, and Accountability*

Upon initial receipt of IMP at the investigational site, the pharmacist or delegated site staff will record the date, details of the bottle, and quantity of capsules.

The investigational sites will be re-supplied with IMPs according to their respective recruitment rates.

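### The compliance screen for the supportive Per-Protocol set has only a lower limit and counts every unreturned capsule as taken, so it cannot itself flag over-use or under-dosing masked by lost capsules

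*SAP*

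**What the plan says.** SAP 5.2 takes the PP set from mITT by two routes. One removes patients with major protocol deviations that could affect efficacy. The other is the compliance screen: "Subjects who are found to be <80% compliant with adrilipase will also be excluded from the PP population". SAP 7.3 repeats it: "subjects found to be <80% compliant with adrulipase will be excluded from the PP population". Neither section gives an upper limit.

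Under SAP 7.3 the dose received is the "number pills dispensed" less the "number of pills returned", times 0.15 g, divided by days on drug. There is no term for lost or discarded capsules. On the denominator it says: "The expected dose for adrulipase depends on whether the subject titrated to a higher dose during the study". It then lists terms for 1.2, 1.95 and 2.4 g/day and none for the 3.3 g/day of Part 2. Its closing note begins: "Note that since capsules are dispensed at one visit and returned at one visit", so one pooled count covers all dose levels.

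Protocol 8.6.1.2 foresees over-use: "Overdose is considered as dose taken above the prescribed daily dose for the current dosing phase". Protocol 8.6.1.4 requires capsule discrepancies to be explained and documented. Both schedules of assessments mark drug return and full accountability at Visit 6 only. Protocol 9.2.4 says of the last visit: "The procedures scheduled for the End-of-Study visit are the same as those that should be conducted for the Early Termination visit"; its list of procedures includes neither return nor count. Protocol 8.6.1.5 has patients return bottles but names no visit.

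**The concern.** A PP set is meant to show whether the result holds among patients who took the drug as planned. Dosing can depart from plan in either direction, and this screen looks in one direction only. It also reads a missing capsule as a swallowed one, so poor accountability raises the score.

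Capsules are issued at Visit 3, Visits 4 and 5 are telephone calls, and the scheduled count is at Visit 6. No interim count can separate over-use, loss and proper use. CFA is summarised by dose level in a study of about 12 patients, so one misclassified patient could matter in a small row. At stake is how far the supportive analysis can be trusted, not the primary result.

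**Working it through.** **Inputs.** Capsules per day are 8, 13 and 16 in Part 1 and 22 in Part 2 (protocol 8.4.1). At 0.15 g each they give 1.2, 1.95, 2.4 and 3.3 g/day, which agrees with the dosing table. The cut-off is <80% (SAP 5.2). I assume 21 treatment days in Part 1 unless stated. The documents give no upper limit, so 110%, 120% and 125% are tried.

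**Step 1: the printed formula.** With L, M and H the days on low, medium and high dose, SAP 7.3 prints the expected dose as 1.2/L + 1.95/M + 2.4 × H. This is not in g/day. For a perfectly adherent patient (a level with zero days is counted as zero):

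| Days L/M/H | Actual g/day | Printed expected | Rate |
|---|---|---|---|
| 21/0/0 | 1.2 | 1.2/21 = 0.057 | 2100% |
| 5/16/0 | (6 + 31.2)/21 = 1.771 | 0.24 + 0.122 = 0.362 | 489.5% |
| 5/5/11 | (6 + 9.75 + 26.4)/21 = 2.007 | 0.24 + 0.39 + 26.4 = 27.03 | 7.4% |

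A day-weighted mean, (1.2L + 1.95M + 2.4H)/(L + M + H), gives 100% in all three rows. The steps below use it. Under the printed form no compliance limit, lower or upper, has a meaning.

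**Step 2: over-use.** Taking the next level throughout:
- 1.2 g/day assigned, 1.95 taken: 1.95/1.2 = 162.5%.
- 1.95 g/day assigned, 2.4 taken: 2.4/1.95 = 123.1%.

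Both pass the lower-only rule. Limits of 110% and 120% flag both; 125% misses the second.

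Partial over-use scores lower:
- Excess on 16 outpatient days, correct dose on 5 days in confinement: low to medium is (16 × 1.95 + 5 × 1.2)/(21 × 1.2) = 37.2/25.2 = 147.6%; medium to high is (16 × 2.4 + 5 × 1.95)/(21 × 1.95) = 48.15/40.95 = 117.6%.
- Correct dose on 5 low days, then high taken on 16 medium days: (6 + 38.4)/(6 + 31.2) = 44.4/37.2 = 119.4%.

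The 117.6% and 119.4% cases pass a 120% limit, so an upper limit alone is not enough.

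**Step 3: lost capsules.** At 16 a day for 20 days, 320 capsules are expected. A patient swallows 60% (192) and loses 64. The formula counts 192 + 64 = 256, and 256/320 = 80%, which is not below 80%, so the patient is kept. In general, a patient passes once the share lost reaches 80% minus the share swallowed. An upper limit does nothing here.

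**Step 4: the pooled count.** With 5/5/11 days and full low and medium dosing, the total needed for 80% is 0.8 × 42.15 = 33.72 g. Low and medium supply 15.75 g, leaving 17.97 g of the 26.4 g due at the high dose, or 68%. A patient can therefore take about two thirds of the high dose and still pass.

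**The case against.** The strongest reply is that the compliance screen is not the only route out of the PP set. SAP 5.2 also removes major deviations, SAP 7.1 has them confirmed at a review before database lock, patients must bring every bottle to Visit 6 (protocol 9.2.2), and the count is verified there (9.2.3). Over-use and loss can be found and acted on. This stands, and it limits the point: the screen does not catch these patients, but they are not bound to stay in. What remains is that neither document says overdose or lost capsules count as a major deviation, so the outcome rests on judgement.

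A reader might go further and infer that these patients' CFA is credited to a lower assigned dose, which would flatter the lower doses. The documents do not support that:
- A patient who lost capsules took less than assigned, so the error runs the other way.
- Grouping is by maximum dose received (SAP 4 and 9.2), and whether that means prescribed level or actual intake is not said. The same grouping applies to mITT, so the PP rule does not cause it.
- CFA comes from supervised confinement with the dose recorded at every meal and snack (protocol 9.2.3). Extra capsules at home need not be the dose behind the measurement.
- Scope is small. When protocol version 2.0 was written, five of six Part 1 patients had been dosed at 2.4 g/day (protocol 6.7), and every Part 2 patient is assigned one dose.

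Nor does the missing count at early termination distort CFA. A patient without a valid post-baseline CFA is outside mITT, and so outside the PP set.

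**Conclusion.** The point holds as a gap in the screen. As specified it cannot flag over-use, and it accepts under-dosing when enough capsules are missing. The 162.5%, 123.1% and 80% results rest on a day-weighted denominator that the SAP does not print, and on a patient staying at one level throughout, which is a simplification because all Part 1 patients start on the low dose. The printed denominator is the larger defect and has to be corrected before any limit can work.

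The impact is minor. The PP set is supportive, no efficacy testing is planned (SAP 9.1.4), and mITT does not use the compliance rate. Bias in CFA by dose is possible but not shown. One reservation: the closing note of SAP 7.3 breaks off mid-sentence in the text available, so a further counting rule there cannot be excluded.

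**What to change.** 1. In SAP 7.3, restate the expected dose as (1.2 × low days + 1.95 × medium days + 2.4 × high days)/total days, in g/day, with a 3.3 g/day term for Part 2. This must come first: with the printed formula, a 120% limit would remove perfectly adherent low-only and low/medium patients.
2. In SAP 5.2 and 7.3, make the PP limit two-sided, <80% or >120%. The 120% is a choice, since the documents give no figure; it catches both single-level steps in the working. Also check the dose recorded during the Visit 6 confinement, for departures that the whole-course rate misses.
3. Treat documented lost or unreturned capsules as unaccounted for. Set compliance to missing and decide PP status at the existing pre-lock review, instead of counting the capsules as taken.
4. In both schedules and protocol 9.2.4, add adrulipase return and count at Visit 7/Early Termination for patients who do not complete Visit 6. This serves accountability and the descriptive compliance summary; it does not touch CFA.

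The cost is some SAP wording and one added procedure at an existing visit. The PP set may lose a patient. The mITT primary analysis does not change.
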